Following an episode of severe hypoglycaemia, standard causes of hypoglycaemia will be reviewed in order to identify an obvious precipitating factor (insulin dosing error, accidental intravascular injection or other injection site problem, excessive unplanned exercise, missed meal, alcohol consumption, renal impairment, loss of warning signs). HbA1c will be repeated where the most recent available value is more than six weeks previously. Where no obvious reversible precipitant is identified, participants will be advised to reduce insulin dose by 10% over the following month and perform more intensive HBGM. At review, after one month, the aim will be to uptitrate insulin dose once again, *unless* glycaemic target HbA1c < 7.0%/ 53 mmol/mol continues to be met on the reduced dose *or* there have been further episodes of major or unacceptable minor hypoglycaemia.

If the participant has a major hypoglycaemic event and is brought into the Emergency Department, this will only be considered an SAE if the hospital stay is longer than 12 hours. Minor hypoglycaemic episodes (i.e those not requiring assistance from another individual) will not be recorded as an AE.

j) Participant discontinuation: Participants will be free to discontinue study medication at any point during the study. Where possible, follow up in the trial will be continued with continuing titration of insulin doses to target. If informed consent for follow-up is withdrawn, data collected up to self-withdrawal will be included in the study unless the participant wishes otherwise. Clinical samples will be destroyed at their request.

k) Source documents: Participants will be asked to provide informed consent for investigators to obtain copies of official documentation (discharge letter or clinic letter) of any cardiovascular events which will be made available at the request of study monitors. This will also apply for Severe Adverse Event reporting (Section 13, page 34 for which we will obtain copies of official documentation (discharge letter or clinic letter).

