12. ASSESSMENT AND REPORTING OF ADVERSE EVENTS / SERIOUS ADVERSE EVENTS

12.1 Definitions

These are in accordance with the Medicines for Human Use (Clinical Trials) Regulations 2004(as amended):

Adverse Event (AE)

Any untoward medical occurrence in a subject to whom a medicinal product has been administered, including occurrences which are not necessarily caused by or related to that product.

Adverse Reaction (AR)

Any untoward and unintended response in a subject to an investigational medicinal product which is related to any dose administered to that subject.

Serious Adverse Event (SAE) or Serious Adverse Reaction (SAR)

Any adverse event or adverse reaction that

- a. results in death
- b. is life threatening
- c. requires hospitalisation or prolongation of existing hospitalisation
- d. results in persistent or significant disability or incapacity
- e. consists of a congenital anomaly or birth defect
- f. is otherwise considered medically significant by the investigator.
- i.e. important adverse events/ reactions that are not immediately life-threatening or do not result in death or hospitalisation but may jeopardise the subject or may require intervention to prevent one of the other outcomes listed in the definition above

Suspected Serious Adverse Reaction (SSAR)

Any adverse reaction that is classed in nature as serious and which is consistent with the information about the medicinal product in question set out in the summary of product characteristics (SmPC).⁵³

Suspected Unexpected Serious Adverse Reaction (SUSAR)

Any adverse reaction that is classed in nature as serious and which is not consistent with the information about the medicinal product in question set out in the SmPC.⁵³

13. RECORDING and REPORTING AEs/SAEs

Adverse events (AEs) will be recorded, notified, assessed, reported, analysed and managed in accordance with the Medicines for Human Use (Clinical Trials) Regulations 2004 (as amended) and as defined within this protocol. (See flow chart)

Metformin is widely available and has been used in the treatment of type 2 diabetes in the UK for more than 50 years, and in the US for more than 10 years. We will therefore collect specific Adverse Events of Medical Interest (see list below): (i) of specific relevance to its potential use in T1DM; (ii) related to the complications of T1DM; and (iii)

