related to the study endpoints. All Serious Adverse Events with exception of planned routine hospitalisations and outpatient hospital visits will be collected within the eCRF.

Adverse Events of Medical Interest

- **Hypoglycaemia:** as per the Steno Hypoglycaemia Questionnaire (Appendix 3) administered at study visits as per the Schedule of Assessments
- **Gastrointestinal:** Diarrhoea, abdominal pain, nausea and vomiting, constipation, loss of appetite resulting in discontinuation of study medication or dose reduction.
- **Cardiovascular:** chest discomfort, palpitations resulting in discontinuation of study medication or dose reduction
- **Any revascularisation:** coronary (angioplasty/ stent/ CABG); carotid (endarterectomy); peripheral (angioplasty/ stent/ surgical)
- **Foot:** ulceration; lower limb surgical procedure: amputation (digit/ below knee/ above knee); ulcer debridement.
- **Eye:** laser treatment; vitrectomy; cataract surgery; vitreous haemorrhage; retinal vein or artery occlusion; loss of vision in one eye.
- **Neurological:** headache resulting in discontinuation of study medication or dose reduction
- **Metabolic:** biochemically-confirmed unexplained acidosis with lactate > 5.0 mmol/L, abnormal LFTS results >2.5 times upper limit of normal, or reduction in eGFR of > 25%
- **Other:** hypersensitivity reaction to metformin, overdose"

As outlined above, the following symptoms **should only be reported as AEs if leading to an SAE or treatment dose reduction/ discontinuation:**

- diarrhoea, abdominal pain, nausea and vomiting, constipation, loss of appetite
- taste disturbance, abnormal stools, nail disorder, rash
- increased sweating, chills, flu syndrome, flushing, skin reactions
- chest pain, palpitations
- headache, myalgia, light-headedness

At all study visits patients will be questioned about any illnesses, hospitalisations and the expected adverse reactions/ events listed above. Completion of patient diaries will aid the research team to elicit adverse events. In addition to adverse event data, at annual visits we will measure liver function tests (AST, ALT and γ GT) and a Full Blood Count.

Full details of AEs of medical interest and SAEs including the nature of the event, start and stop dates, severity, relationship to study drug and outcome will be recorded in the subject's medical records and in the eCRF. AEs will be monitored and followed up until satisfactory resolution or stabilization.

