2.4.5.3. SERIOUS ADVERSE EVENTS

The number of serious adverse events will be reported overall and by treatment group for any event, and by classifications of expectedness, relationship to study medication, severity and outcome.

The number and percentage of patients experiencing at least one adverse event will be reported overall and by treatment group for all events, and for events classified by MedDRA System Organ Class and Preferred Term.

A by subject listing of serious adverse events will also be provided.

Listings of all deaths will also be provided.

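### The 12-hour rule for emergency-department hypoglycaemia contradicts the protocol's own definition of a serious adverse event, so the SAE count can only be too low

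*Protocol*

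**What the plan says.** Three parts of the protocol bear on whether a major hypoglycaemic episode is an SAE.

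- **Section 7.3(i), hypoglycaemia management plan.** The rule opens "If the participant has a major hypoglycaemic event and is brought into the Emergency Department" and continues "this will only be considered an SAE if the hospital stay is longer than 12 hours".
- **Section 12.1, definitions.** An event is serious if it meets any one of six criteria. They include that it "results in death", "is life threatening", "requires hospitalisation or prolongation of existing hospitalisation", or "is otherwise considered medically significant by the investigator". The other two are lasting disability and congenital anomaly.
- **Section 13, recording and reporting.** The collection rule is "All Serious Adverse Events with exception of planned routine hospitalisations and outpatient hospital visits will be collected within the eCRF". SAEs must be entered in the eCRF within 24 hours of the site learning of them, and assessed for seriousness, causality, severity and expectedness.

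SAP 2.4.5.3 then builds on that classification: "The number of serious adverse events will be reported overall and by treatment group".

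Major hypoglycaemia is also counted whatever its SAE status. The Steno questionnaire (Protocol Appendix 3) collects it, SAP 2.4.2 makes its frequency a tertiary outcome with a negative-binomial analysis, and SAP 2.4.5.4 lists it as an event of particular interest.

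**The concern.** The word *only* in 7.3(i) makes length of stay the sole test of seriousness for these episodes. Sections 12.1 and 13 do not refer to that rule or make room for it, so for some episodes a site cannot follow both.

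What is at stake is what SAE status sets in motion: prompt eCRF entry, causality and expectedness assessment (on which SUSAR reporting depends) and a place in the SAE tables by arm. Protocol Section 8 accepts that metformin combined with insulin may carry a small additional risk of hypoglycaemia, and all participants have insulin titrated towards a glycaemic target. Serious hypoglycaemia is therefore a foreseeable harm in this trial, and its classification should not depend on which section a site happens to follow.

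**Working it through.** No figure in the plan can be recalculated. The only number is the 12-hour threshold, and the documents give no derivation for it. The check sets the rules side by side for a major episode brought to the Emergency Department with a stay of 12 hours or less.

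| Short-stay episode | Under 12.1 | Under 7.3(i) |
|---|---|---|
| Fatal | SAE, criterion (a) | Not an SAE as literally worded |
| Life threatening, for example a coma so judged | SAE, criterion (b) | Not an SAE |
| Unplanned admission, discharged by 12 hours | SAE, criterion (c) | Not an SAE |
| Leaves lasting disability | SAE, criterion (d) | Not an SAE |
| Judged medically significant by the investigator | SAE, criterion (f) | Not an SAE |
| Attendance without admission, no criterion met | Not an SAE | Not an SAE |

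**Direction.** Let N be the number of SAEs under 12.1 and k the number of short-stay episodes in the first five rows, each counted once. The count under 7.3(i) is N − k with k ≥ 0, so it can never exceed the count under 12.1.

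**Size.** k cannot be calculated. The documents give no rate of major hypoglycaemia, of Emergency Department attendance or of short stays.

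**Comparison between arms.** Suppose a share q of hypoglycaemia SAEs is lost in each arm, with true expected counts A and B. The recorded expectations are (1 − q)A and (1 − q)B. Their ratio is still A/B, and their difference shrinks to (1 − q)(A − B). A distorted ratio for these events would need q to differ between arms, and the documents give no information on that.

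**Consistency.** The 7.3(i) rule applies only to participants brought to the Emergency Department. A clinically similar episode treated elsewhere stays under 12.1, so seriousness depends on where the episode was treated.

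**Whether other data restore the classification.**
- The questionnaire records numbers of events with and without coma, average glucose, potential cause and treatment. It has no field for admission, length of stay or seriousness.
- Section 13 names hypoglycaemia among the Adverse Events of Medical Interest and asks for severity, relationship to study drug and outcome. The corresponding list in SAP 2.4.5.2, where relationship and seriousness are summarised, omits hypoglycaemia.
- SAP 2.4.5.4 plans counts and percentages of major events, not their seriousness or causality.

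**The case against.** The strongest defence is that the sentence sits in a management plan, speaks of a hospital stay, and only separates an emergency visit from an admission. Section 13 already leaves outpatient hospital visits out of SAE collection. This is a sensible purpose and it could account for criterion (c). It does not account for death, life-threatening events, disability or medical significance, none of which turns on length of stay.

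The second defence is that the comparison of hypoglycaemia between arms is largely handled elsewhere: a formal tertiary analysis, separate counts with and without coma, and an event-of-interest summary. That stands, and it confines the problem to SAE classification and reporting. Section 7.3(i) also asks participants to report major episodes to the site within 24 hours during dose titration, but that is notice to the site team, not SAE entry in the eCRF.

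A reader might also infer more than the documents support:

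- **That every short attendance is lost from the SAE count.** Only those meeting a 12.1 criterion are.
- **That the rule biases the SAE comparison towards no difference.** It applies equally to both arms of a double-blind trial, no differential loss is shown, and Protocol Section 15 has adverse events summarised without formal comparison.
- **That a 24-hour deadline for the pharmacovigilance database is missed.** The 24-hour limit is for site entry into the eCRF. Section 13 gives no time limit for the later transfer.
- **That hypoglycaemia is the main expected harm.** Section 8 describes a possible small additional risk and calls gastrointestinal effects the most common.

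**Conclusion.** The contradiction is real and follows from the text alone. Read as written, 7.3(i) removes from SAE status short-stay Emergency Department episodes that 12.1 defines as serious. The direction is certain: the SAE count is too low or, if no such episode occurs, unchanged. The size and any imbalance between arms are unknown.

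The conclusion assumes that sites apply 7.3(i) literally. If some follow 12.1 instead, the shortfall is smaller but classification differs between sites. The primary and secondary outcomes and the planned analysis of hypoglycaemia frequency are not affected. The point concerns the completeness of serious-event reporting, and the sections need to be reconciled.

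**What to change.** Reconcile Protocol 7.3(i), 12.1 and 13:

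1. Limit the 12-hour sentence to deciding whether an Emergency Department attendance counts as hospitalisation under criterion (c).
2. State in the same place that all other criteria in 12.1 still apply whatever the length of stay. Medical significance should stay with the investigator, as 12.1 provides. Classing every episode with unconsciousness as medically significant would be a new rule and is not needed to remove the contradiction.
3. Before database lock, have sites reassess against 12.1 the recorded major episodes that involved an Emergency Department attendance, and complete SAE forms where a criterion is met.

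The wording change is small. The reassessment needs source records, because the questionnaire holds neither admission nor length of stay. Section 7.3(k) provides for obtaining discharge or clinic letters for cardiovascular events and serious-event reporting, so letters for episodes not classed as serious may still have to be requested. The number of additional SAE forms cannot be estimated from the documents. Treatment of participants does not change.

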8. MEDICATIONS

Formulation, source and labelling of study medication. The Investigational Medicinal Product (IMP) in the study is metformin 500mg or matching placebo tablets. The metformin tablet is identical in chemical composition to Glucophage 500mg licensed in the UK. See the Summary of Product Characteristics for further details.⁵³ The matched placebo will be formulated as film-coated tablets matching Glucophage 500 mg tablets (tablet core - cellactose, calcium hydrogenphosphate, magnesium stearate; film coating – hypromellose). Metformin 500mg and placebo tablets will be manufactured in accordance with Good Manufacturing Practice. Both active and placebo medication will be packaged and distributed by Merck-Serono® and supplied to study sites free-of-charge.

The single-blind run-in packs will contain sufficient supplies for 28 days treatment. For the double-blind treatment period, metformin 500 mg and matching placebo tablets, will be packed in matching packs so as to maintain the blind. Each pack contains sufficient supplies for 90 days' treatment with a small overage (excess). Packs will be labelled with a unique pack number that will be used to assign treatment to the patient via the IVRS/IWS system whilst maintaining the blind. Packs will be labeled in accordance with Good Manufacturing Practice and local regulatory requirements. Labelling text will include protocol identification reference, storage caution statements, dosing instructions, batch number and expiry date. A tear-off label will be attached for dispensing purposes.

Drug storage and stability. All study drug must be stored in the original container below 30°C in a secure location. Although the investigator is ultimately responsible for ensuring that all study drug received at the site is inventoried and accounted for throughout the study this should be delegated to an appropriately trained pharmacist at the site who will be responsible for the accountability of all used and unused trial supplies. The study drug must be stored in accordance with the study medication label. The study medication provided for use in the study will be used only as directed in the study protocol and only for trial participants.

Drug ordering. Study drug will only be released to the study site once all the appropriate regulatory and governance approvals are in place. The IVRS/IWS will track drug supplies at individual study sites and trigger additional drug supply shipments when required.

Drug accountability. A record of study drug movements will be maintained for accountability purposes. Delegated pharmacy staff will be required to receipt the drug via the IVRS/IWS system and record the dispensing of the study drug to participants on appropriate drug accountability forms. Study drug should not be dispensed or supplied to patients without the appropriate IVRS/IWS notifications being completed. Drug accountability records will include the use by each patient, disposal of patient returned medicines and any unused study medication. Accountability records will include dates, quantities, batch numbers, expiration dates and the unique code numbers assigned to the investigational medicinal product and study participants.

Only those supplies intended for use in the study will be dispensed to study participants. Unused study drug will be disposed of in accordance with the guidance in the “Disposal” section below. Study drug will not be used for any purpose other than the present study. Study participants must be instructed to return all original containers including empty, partially filled or unused medication at the end of each treatment period in order that an assessment of medication adherence can be performed.

Accountability logs will be made available for inspection by the study sponsor or their designee and regulatory inspectors. Sites may be required to send anonymised accountability log information to permit remote site monitoring. Study sites will be provided with appropriate drug accountability logs and further detailed written information on study drug management.

Maintaining blinding. Study medication will be assigned electronically or by IVRS (Interactive Voice Response System) supplied by the Robertson Institute for Biostatistics, see section 14.1.

Unblinding. Ceasing treatment, rather than unblinding, will be carried out as far as possible. In any case of hospitalisation with acute illness participants will be advised to discontinue the study medication and inform the relevant clinician. However, where knowledge of treatment may assist emergency treatment, unblinding will be supported. Study participants will be provided with a Patient Alert Card indicating the name of the investigational study drug, the study number, the investigator’s name, a 24-hour contact number and information on how to unblind in an emergency: a freephone number will be provided which permits this via a telephone menu system. Several prompts in the system warn the user that they require to be a health professional and to record their name and other pertinent information. For each unblinding an email alert is generated to the Study Coordinator and Chief Investigator. Requests are set at a maximum of 2-3 per 24 hours in case of malicious unblinding. The most likely scenarios for unblinding will be:

confirmed pregnancy, overdose/ accidental ingestion, development of acute renal failure. The Patient Alert Card will be collected from patients at the end of their involvement in the study.

Route of administration. Tablets should be taken orally and swallowed with a glass of water and food (at mealtime).

Double-blind treatment periods dose and dose titration. Metformin as Glucophage 500mg two tablets twice daily (= 1000mg twice daily) or matching placebo tablets. Participants will be asked to titrate up the medication according to usual practice with metformin i.e. they will take one tablet with the evening meal for one week; this will then be increased to additional tablets at weekly intervals with the morning meal, evening meal and then morning meal until a dose of 1000 mg twice daily is achieved. This dose titration, and any insulin adjustment required, will be supported by the weekly telephone calls and guidance printed in the Study Diary. Participants will also be able to call study nurses. If it is found that a participant is only able to tolerate a lower daily dose of study medication, in particular due to gastrointestinal side-effects (see below), this will be permissible and will be documented accordingly.

Risks of treatment. Please refer also to the SmPC.⁵³

- Lactic acidosis (blood pH <7.35 with plasma lactate >5.0 mmol/L): This condition has been associated with metformin, usually in cases of acute renal failure, but there remains no evidence that metformin causes lactic acidosis in stable individuals with adequate renal function.^{23,24} The reported incidence of lactic acidosis in patients receiving metformin hydrochloride is very low (approximately 0.03 cases/1000 patient-years, with approximately 0.015 fatal cases/1000 patient-years) and in 8.4 vs 9.0 cases per 100,000 patient years MF vs other diabetes medications of placebo (www.ahrq.gov – Johns Hopkins). In more than 20,000 patient-years exposure to metformin in clinical trials, there were no reports of lactic acidosis. Risk factors are significant renal insufficiency, liver dysfunction, severe acute congestive heart failure and any state where there is risk of hypoperfusion and hypoxaemia.
- Hypoglycaemia: metformin without concomitant diabetes medications has not been shown to cause hypoglycaemia. However, in combination with insulin therapy, there may be a small additional risk, although neither minor or major overall hypoglycaemia risk was statistically elevated in the largest previous trial.¹⁸ Participants will be informed of the symptoms of hypoglycaemia, namely skin pallor, trembling, perspiration, a feeling of weakness and/or hunger, blurred vision and advised to take appropriate corrective measures e.g. sugar-containing drink or food.
- Pregnancy and lactation: metformin is increasingly considered safe in pregnancy²⁵ but will be an exclusion criterion in this study [see Section 7.3(c)].
- Renal dysfunction: Metformin is excreted renally and may therefore accumulate during significant renal dysfunction. Therefore renal function will be assessed by regular U&E analyses during the trial. Intravascular administration of iodinated contrast agents in particular (e.g. coronary or peripheral angiograms, contrast imaging such as CT scans) may precipitate renal failure with resultant accumulation of metformin. Therefore standard procedures will be followed in such circumstances: the study drug will be discontinued prior to the test and not reinstated until >48 hours later only after it has been verified that renal function has returned to pretest levels.

Choice of eGFR threshold (45mL/min/1.73m²) in study: Metformin is commonly used safely in patients with moderate chronic renal impairment. In one example in Tayside,⁵⁴ 4.8% of patients on metformin in Tayside had a serum creatinine >150umol/L with one case of lactic acidosis in 4600 patient years; that case was related to acute myocardial infarction with secondary acute renal failure and not due to metformin therapy. In another study from Edinburgh,⁵⁵ researchers concluded that an eGFR threshold between 36 – 40mL/min/1.73m² would be useful and safe. The UK National Institute for Clinical Excellence published criteria for use of metformin in chronic renal impairment in 2008.⁵⁶ This guidance states that metformin is contraindicated with a serum creatinine >150 micromol/L or eGFR <30 ml/minute/1.73 m². Furthermore the guideline recommends that the dose of metformin be reviewed if the serum creatinine exceeds 130 micromol/L or the eGFR is below 45 ml/minute/1.73 m².

Accordingly, we have selected a baseline eGFR threshold of 45mL/min/1.73m² in this study below which participants will not be recruited. If during participation a subject's eGFR falls to <45mL/min/1.73 m² consideration will be given to IMP dose reduction. If during participation a subject's eGFR falls to <30mL/min/1.73 m² IMP will be discontinued.

Side effects. Please refer also to the SmPC.⁵³

- Very rare (<1/10 000): Chest discomfort, palpitation. These should only be recorded as AEs if associated with an SAE, or if they result in discontinuation of study medication or dose reduction.

- Common (>1/100): taste disturbance, abnormal stools, hypoglycaemia (see below), myalgia, lightheadedness, dyspnoea, nail disorder, rash, sweating increased, chills, flu syndrome, flushing, skin reactions. These should only be recorded as AEs if they result in discontinuation of study medication or dose reduction.

- Common (> 1/100): Decreased vitamin B12 absorption has been reported in long term use, however although plasma levels fell significantly in the HOME trial over 4.3 years,¹⁷ actual levels usually remained within standard reference ranges. Vitamin B12 Serum levels falling below the local assay reference range (150 pmol/L or equivalent) should be recorded as AEs.

- Very common (>1/10): Gastrointestinal effects are most common and may include nausea, vomiting, diarrhoea, abdominal discomfort, headache and loss of appetite. It is well recognised that these side-effects usually resolve spontaneously following initiation of therapy and are minimised if the dose is titrated upwards (as will be done in the study). These events should only be recorded as AEs if they result in discontinuation of study medication or treatment dose reduction.

Serious Adverse Reactions that are expected (<0.5%)

- Lactic acidosis may occur extremely rarely (see page 28 above). It will usually be associated with hospitalisation and reported as an SAE.

Abnormal Laboratory Findings

The following will be specifically recorded as AEs on CRF pages:

- LFTs: any abnormal results of >2.5 times upper limit of normal
- Reduction in eGFR to < 45 ml/min/1.73 m² and < 30 ml/min/1.73 m²
- Hb < 10.0 g/dL AND fall of >1.5 g/dL from baseline
- MCV > 105 fL

Other. Participants will be advised to avoid alcohol excess during the study though this is not an exclusion criteria. Their primary care physician (where applicable) will be

advised that if commencing a medication which may lead to a deterioration in renal function, such as NSAIDs, they should monitor renal function and advise the study doctor of any deterioration.

Interruption of treatment: in preference to permanent treatment withdrawal or withdrawal from the study, investigators will permit treatment interruption of any duration (which will be documented) in any participant who develops any of the following:

- Acute illness: severe infection, shock, acute or clinically unstable cardiac failure
- Acute myocardial infarction or other acute coronary syndrome
- Surgery: treatment will be discontinued 48 hours prior to elective surgery with general anaesthesia and will be recommenced no earlier than 48 hours following surgery and only when it has been confirmed that renal function has returned to pre-operative levels.
- Requirement for investigation involving intravascular iodine-containing contrast agent (as per national guidelines): treatment will be discontinued 48 hours prior to investigation and recommenced no earlier than 48 hours afterwards.
- Anaemia (Hb<10.0 g/dL AND fall of >1.5 g/dL from baseline) considered by the local investigator to be potentially related to study medication.

In these cases, treatment will be restarted where possible in accordance with the Investigator's clinical judgement, local practice, standard-of-care, and national guidelines (renewed titration from a lower starting dose is not usually required unless interruption has been prolonged e.g. more than four weeks). Where treatment interruption has persisted for four weeks or more it will be documented as permanent.

Withdrawal of treatment: Investigators will withdraw from treatment any participant who develops any of the following:

- Pregnancy: discontinue if participant becomes, or intends to become, pregnant
- Development of new contraindications to metformin
 - o hepatic impairment (ALT > 3.0 ULN)
 - o renal impairment with eGFR <30 mL/min/1.73m² during study – see page 28
- Biochemically-confirmed severe lactic acidosis (>5.0 mmol/L with acidosis)
- Hypersensitivity to metformin

Dose reduction of treatment: Where eGFR falls below 45 ml/min/ 1.73m² on any measurement Investigators should permanently reduce metformin dose to 500 mg twice daily.

Withdrawal from study: Investigators will withdraw from the study any randomized participants with:

[figure not shown]
- confirmed pregnancy
- withdrawal of consent for follow-up
- any other reason agreed between the participant and the site Principal Investigator

At the end of the study: No further study medication will be provided.

Assessment of adherence: Tablet counts will be carried out by study nurses following at relevant study visits, including the final clinic visit, to assess adherence. This will be documented in the eCRF. Site medical and nursing staff will also discuss and reinforce adherence to study medication with participants.

Concomitant medication. No concomitant medication is specifically excluded.

